5.7 Disease Characteristics

Treatment Failure of Prior Migraine Preventive Medications

Treatment failure of prior migraine preventive medications is determined by “Reason for Stopping” as “Lack of efficacy” or “Adverse reaction” on the Prior Migraine Prophylactic Medication eCRF.

Menstrual-related migraine

If a female patient responds yes to the question “Does the subject report migraine attacks that occurred on day 1 +/- 2 of menstruation (ie Days -2 to +3, day 1 = start of menstruation) in at least two out of the last three menstrual cycles prior to screening?” in the Headache and Migraine Frequency History eCRF then the patient will be considered in the subgroup menstrual-related migraine.

6. Analysis Sets

6.1 Full Analysis Set

The full analysis set (FAS) consists of all subjects who enroll in the study. Analysis of disposition, demographic and baseline characteristics, and important protocol deviations (IPD) will utilize the FAS.

6.2 Safety Analysis Set

The safety analysis set (SAS) will consist of a subset of subjects in FAS who receive at least 1 dose of investigational product. Analysis for safety endpoints and summary of investigational product administration will utilize the SAS.

6.3 Study-specific Analysis Sets

6.3.1 Observed Data Analysis Set

The observed data analysis set consists of a subset of subjects in FAS who receive at least 1 dose of investigational product and have an observed value for the endpoint of interest and pass the quality control procedures of genetic analysis. Primary analysis of

the efficacy endpoints related to the genetic biomarkers will utilize the observed data analysis set. Details of this analysis set is mentioned in the analysis plan developed by deCODE.

6.3.2 Efficacy Analysis Set

The efficacy analysis set (EAS) consists of a subset of subjects in FAS who receive at least 1 dose of investigational product. Primary analysis of the exploratory efficacy endpoints will utilize **observed data for subjects in** the EAS.

7. Planned Analyses

7.1 Interim Analysis and Early Stopping Guidelines

Not applicable.

7.2 Primary Analysis

The primary analysis (or final analysis, as this study has only 1 milestone analysis) will be performed after all subjects have completed their week-24 or end-of-study visit. The data will be cleaned, and the database will be locked for the primary analysis.

8. Data Screening and Acceptance

8.1 General Principles

The objective of the data screening is to assess the quantity, quality, and statistical characteristics of the data relative to the requirements of the planned analyses.

8.2 Data Handling and Electronic Transfer of Data

[figure not shown]
The Amgen Global Study Operations-Data Management (GSO-DM) department will provide RAVE database, **data outside of RAVE database** (eDiary data and biomarkers). The database will be subjected to edit check outlined in the Data Management Plan (DMP). Additional details **for data outside of RAVE** will be provided in the DMP and Data Acquisition Requirements Specification (DARS).

8.3 Handling of Missing and Incomplete Data

Subjects may miss specific data points for a variety of reasons. In general, data could be missing because of a subject's early withdrawal from the study, a missed visit, or inability to evaluate an endpoint at a time point. For this study, efficacy endpoints will be collected via eDiary and subjects could miss entering several days of data in each monthly interval. The general procedures outlined below describe how missing data will be handled.

For the eDiary data, if at least 14 days of eDiary are collected in the monthly interval, then the monthly frequency measurements (eg, migraine days or acute migraine-specific

medications days [AMSMED] will be prorated based on the number of days with available

The analysis of **all efficacy and safety** endpoints will be performed **by using observed data only**. Missing **efficacy** assessments (eg, **MMD**, **MFIQ** etc.) will not be imputed.

Missing safety endpoints will not be imputed. Missing or incomplete dates will be listed as reported, except for incomplete start date of an adverse event or concomitant medication ([Table 5](#)).

Table 5 Imputation for Incomplete Start Date of an Adverse Event or Concomitant Medication

Missing	Imputation	Exception on Adverse Event Start Date
Day	01	Default to study day 1 if an adverse event started the same year and month as study day 1 and the flag indicates that the adverse event started on or after the first dose of investigational product on the Events eCRF
Day/Month	01 Jan	Default to study day 1 if an adverse event started the same year as study day 1 and the flag indicates that the adverse event started on or after the first dose of investigational product on the Events eCRF
Day/Month/Year	None	—

eCRF = electronic case report form

Imputation Rules for Missing IP administration Dates of the last IP dose

If the date of last exposure treatment weeks is partial or entirely missing but receiving IP is confirmed, impute the date by the study Day 1 + last exposure treatment weeks * 7 days. Ensure the imputed last exposure to treatment date is on or before the end of study date.

Imputation of missing genotype data

The details for the imputation of genotype data will be described in the deCODE Analysis Plan (Appendix B).

8.4 Detection of Bias

The factors that may bias the results of the study include:

- important protocol deviations likely to impact the analysis and interpretation of the efficacy endpoints
- investigational product dosing non-compliance
- the timing of and reasons for early withdrawal from treatment and from study

The incidence of these factors may be assessed. Important protocol deviations will be tabulated **and/or** listed.

The reasons for early withdrawal from treatment and from study will be tabulated and/or listed.

8.5 Outliers

Histograms will be examined to identify outliers in any of the continuous variables used in the analyses. Unexpected and/or unexplained values in categorical data will be identified by utilizing frequency tables.

Outliers due to data entry errors will be corrected by the study team before final database lock. The validity of any questionable values or outliers will be confirmed.

Outliers or any questionable values with confirmed validity will be included in the analyses presented in this statistical analysis plan unless there is sufficient justification to exclude them. However, ad-hoc sensitivity analyses may be conducted to evaluate the influence of extreme values in the data.

8.6 Distributional Characteristics

Continuous endpoints of change from baseline value will be analyzed under normality assumption. **Transformations may be used if necessary. For example, baseline CGRP levels will be log-transformed before analysis if high skewness is present.**

8.7 Validation of Statistical Analyses

Programs will be developed and maintained, and output will be verified in accordance with current risk-based quality control procedures.

Tables, figures, and listings will be produced with validated standard macro programs where standard macros can produce the specified outputs.

The production environment for statistical analyses consists of Amgen-supported versions of statistical analysis software; for example, the SAS System version 9.4 or later.

9. Statistical Methods of Analysis

9.1 General Considerations

Summary statistics will be tabulated at each assessment time point, as applicable. For continuous endpoints, the descriptive statistics include the following: number of observations, means, medians, standard deviations, standard errors, first and third quartiles, minimums and maximums, and 2-sided 95% CIs of the means (CIs will be provided for efficacy endpoints only). For categorical endpoints, the summaries will contain the number and percentage of subjects in each category.

The primary (or final) analysis for the study will be performed on a locked database after all subjects have completed the study or discontinued from the study.

Weighted Bonferroni adjustment will be used to maintain a family-wise error rate of 0.05 (2-sided) for primary endpoint. Analyses involving endpoints related to genetic features will be performed by deCODE.

Summary of efficacy endpoints by treatment group will be based on treatment received on study day 1. Dose **switching** between 70 mg and 140 mg erenumab are permitted at the week 12 visit per investigator's discretion.

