9.3.2.2 Efficacy Analyses

Endpoint	Statistical Analysis Methods
Primary	A GWAS of Icelandic and Danish data will be performed using logistic regression for binary phenotypes. Assuming an additive model, GWAS will be performed for overall sample and by pre-specified subgroups, in addition to other phenotypes of interest that may be defined from the study data. Age and sex will be used as covariates in Icelandic associations and age, sex, and 10 principal components will be used as covariates (to account for population structure) in Danish data. Linkage disequilibrium (LD)-score regression will be used to account for inflation in test statistics due to cryptic relatedness and stratification. A likelihood-ratio test will be used to compute all P-values. The Icelandic and Danish GWAS will be meta-analyzed using a fixed effects model. Weighted Bonferroni adjustment will be used to maintain a family-wise error rate of 0.05 (2-sided) for primary endpoint. Using summary statistics from these studies (excluding GWAS data from Denmark and Iceland), migraine polygenic risk scores (mPRS) will be calculated for the individuals participating in the clinical trial by summing their identified risk alleles, weighted by effect sizes and accounting for linkage disequilibrium using the LDpred software package. This analysis is planned to be performed by deCODE and details of the analysis are described in deCODE Analysis Plan (Appendix B of the statistical analysis plan).
Exploratory	The analyses will be described in the statistical analysis plan, which will be finalized before database lock.

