9.7 Other Analyses

9.7.1 Analyses of Biomarker Endpoints

Summary statistics will be provided for **baseline** CGRP Biomarker **measurements**.

Endpoints related to **baseline** CGRP **measurements** have been described in Section 9.5.2 and [Tables 7 & 8](#).

10. Changes From Protocol-specified Analyses

The proteomics analyses performed by deCODE are not specified in the protocol but will be performed and included in the final CSR.

The primary endpoint analyses have evolved based on deCODE's recommendation. We will no longer present summaries for any genetic variant that is found to be statistically associated with a 50% reduction in MMD over months 4, 5, and 6. Instead, we will only consider associations for a pre-determined set of genetic variants, where these genetic variants will be selected because they have shown genome-wide significant association with migraine in previous studies (~135 SNPs total expected). The reasoning for this change is that the Bonferroni threshold to determine statistical significance will be stricter if we considered all genetic variants ($0.05/1,000,000 = 5E-8$) than if we only considered a subset of genetic variants (using 135 SNPs gives a threshold of $0.05/135 = 3.7E-4$). This will substantially improve power to detect statistical significance for individual genetic variants.

11. Literature Citations / References

12. Prioritization of Analyses

Prioritization of analyses has not been identified at this time.

13. Data Not Covered by This Plan

The Global Biostatistical Science department will not perform any analyses using genomics or proteomics data in this study and will not analyze post-baseline CGRP data at this time.

14. Appendices

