Analysis of primary and exploratory objectives will be performed by deCODE. Amgen will provide the subject level clinical endpoints and covariates of interest to be analysed in relation to mPRS, sequence variants, and proteins. The analysis set for all deCODE performed analyses consists of individuals who receive at least one dose of investigational product, have an observed value for the endpoint of interest, pass all quality control procedures, and who are determined to be of Icelandic or Danish ancestry based on admixture analysis. Age, sex, dose switch (yes/no), and the baseline value of the clinical endpoint of interest (when applicable) will be used as covariates in all analyses. Additionally, principal components will be included as covariates in all Denmark related genomic analyses to account for population structure. Analyses will be run both with and without the dose switch (yes/no) and baseline clinical value

covariates to assess model robustness. All described analyses will be run separately in the Iceland and Denmark samples, and subsequently combined in a meta-analysis.

Genomic analyses will focus on a subset of 136 migraine variants found to be associated with migraine in previous literature instead of genome-wide analyses (9, 23). The rationale for focusing on this subset of migraine variants is to substantially reduce the multiple testing burden, since a Bonferroni genome-wide significance threshold = 5E-8 and a Bonferroni corrected threshold for the migraine variant subset = 0.05/136 = 3.7E-4.

Primary objective

To explore the relationship between clinical response to erenumab and genetic/proteomic biomarkers

Endpoint:

Achievement of at least a 50% reduction from baseline in mean monthly migraine days (MMD) over months 4, 5, and 6 in relation to each individual genome-wide significant single-nucleotide polymorphism (SNP) contributing to the migraine polygenic risk score (mPRS).

Method:

Test for association using logistic regression between migraine variants and the mPRS and whether individuals treated with erenumab achieve 50% reduction from baseline in MMD over months 4, 5, and 6. Individuals who do not achieve at least a 50% reduction are considered controls and those who achieve a least a 50% reduction are considered cases.

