Test for association between the mPRS and the specified MFIQ endpoints using linear regression. See Exploratory Objective 1.

Methods:

Association analysis and meta-analysis.

Genomic associations will only be assessed for SNPs previously validated as being genome-wide associated with migraine. This comprises 136 SNPs to date (9, 23), and this list will be updated with any additional migraine SNPs that may be published at the time of analysis. Associations will be assessed separately in each sample (Iceland, Denmark) and then combined in a meta-analysis. A Bonferroni correction will be used to account for multiple testing.

Calculation of migraine polygenic risk scores (mPRS)

Complex traits such as migraine, are affected by many genes and sequence variants, most of which have a small effect on disease risk (8,9). Polygenic scores can be constructed for any complex genetic phenotype for which a GWAS is available, such as from the large migraine GWAS meta-analyses by Gormley et al. including 375,000 individuals (8) and the most recent, even larger (approximately 1 million individuals) by Hautakangas et al (9). The migraine polygenic risk score (mPRS) will be calculated using migraine GWAS summary statistics from the largest cohorts available to deCODE genetics at the time of analysis (excluding data from Denmark and Iceland). The polygenic risk score (mPRS) values can then be calculated for the individuals participating in the clinical trial by summing their identified risk alleles, which are weighted by effect sizes derived from the GWAS results (8). Linkage disequilibrium will be accounted for using the LDpred software package (10). Principal components will be used to account for population structure within Denmark. No overlap between training and testing datasets is essential to maintain independence of predictions, and the removal of related individuals is also needed, as demonstrated and described in detail by Wray et al. (11).

Effect of sequence variants on levels of plasma proteins and CGRP.

Proteins (n=~7,000) in plasma samples from the study participants will be measured using SomaLogic® (SomaLogic, Inc.) as described elsewhere (16,17). In short, aptamers are modified to recognize specific

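### The rule for declaring a SNP associated with response is not unique: the Bonferroni weights are unstated, the SNP list has no freeze date, and dose switch enters the primary model unrecorded

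*SAP*

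**What the plan says.** SAP 9.5.1 makes the primary result the set of migraine SNPs significantly associated with 50% response over months 4 to 6. Protocol 9.3.2.2, SAP Table 6 and SAP 9.5.1 all send the reader to Appendix B for the details. The rule behind that result is spread over several places.

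- **Threshold.** SAP 9.1: "Weighted Bonferroni adjustment will be used to maintain a family-wise error rate of 0.05 (2-sided) for primary endpoint". Protocol 9.3.2.2 has the same sentence. Neither gives weights. SAP 10 instead says that "using 135 SNPs gives a threshold of" 3.7E-4, and Appendix B gives a "Bonferroni corrected threshold for the migraine variant subset = 0.05/136 = 3.7E-4".
- **SNP list.** SAP 10: "we will only consider associations for a pre-determined set of genetic variants", with about 135 expected. Appendix B counts 136 to date and adds that "this list will be updated with any additional migraine SNPs that may be published at the time of analysis". On timing, SAP 9.1 says: "The primary (or final) analysis for the study will be performed on a locked database after all subjects have completed the study".
- **Model.** Protocol 9.3.2.2: "Age and sex will be used as covariates in Icelandic associations and age, sex, and 10 principal components will be used as covariates" for Denmark. Appendix B: "Age, sex, dose switch (yes/no), and the baseline value of the clinical endpoint of interest" are covariates in all its analyses, plus principal components in Denmark. It then repeats the analyses without dose switch and baseline value, as a check of robustness.
- **Status.** Protocol 3.2 and SAP 2.2 say that nothing is formally tested and that all analyses are descriptive.

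**The concern.** A primary result that consists of SNPs passing a threshold needs one threshold, one list and one model, all settled before the response data are analysed. Here two analysts who start from different passages could each say they followed the plan and still report different SNPs.

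Dose switch raises a further question. SAP 5.5 defines it as any change from the baseline dose during the study, so it is known only after treatment starts. The protocol leaves the week 12 change to the investigator's discretion. If changes tend to follow poor early response, and a SNP affects early response, then dose switch lies between the SNP and the month 4 to 6 outcome. Conditioning on it can remove part of the effect that the study wants to find.

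**Working it through.** **1. The plan's own thresholds.** 0.05/135 = 3.70E-4 and 0.05/136 = 3.68E-4. Both round to the stated 3.7E-4, so 135 against 136 is immaterial. Both are equal splits, and they agree with the weighted rule in SAP 9.1 only if every weight is 1, which no passage says.

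**2. What weights could do (illustration).** The inputs from SAP 3.2 are n = 1400 × 0.9 = 1260, response 50%, allelic odds ratio 1.8 and lowest MAF 0.1. The expected test statistic is ln(1.8) × √(1260 × 0.25 × 2 × 0.1 × 0.9) = 0.588 × √56.7 = 4.43. Power is Φ(4.43 − critical z).

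| Assumed weight | Threshold | Critical z | Power |
|---|---|---|---|
| 0.5 | 0.025/136 = 1.84E-4 | 3.740 | 75% |
| 1 | 0.05/136 = 3.68E-4 | 3.562 | 81% |
| 2 | 0.10/136 = 7.35E-4 | 3.376 | 85% |

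A simulation of the likelihood-ratio test without covariates gave 72%, 79% and 84%, so the approximation is 1 to 3 points high. The weights are assumptions; the documents propose none.

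**3. The list and the divisor.** Protocol 9.3 has the SAP final before lock, SAP 9.1 puts the analysis after lock, and Appendix B keeps the list open to the time of analysis. The family can therefore change after lock, and no freeze date is given. For the error rate, K × 0.05/K = 0.05 for any K. With an assumed growth to 150 SNPs, the threshold becomes 0.05/150 = 3.33E-4 and the bound stays at 0.05. Only if 0.05/136 were kept would the bound be 150 × 0.05/136 = 0.055.

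**4. The covariate sets side by side.**

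| Source | Age, sex | Principal components | Baseline value | Dose switch | Other |
|---|---|---|---|---|---|
| Protocol 9.3.2.2 | yes | 10, Denmark | no | no | – |
| Protocol 9.2.2 (all adjusted efficacy models) | – | – | yes | – | – |
| SAP 4.1 (change-from-baseline models) | yes | mPRS analyses | yes | yes | baseline dose |
| Appendix B, stated set | yes | Denmark, number not given | yes | yes | – |
| Appendix B, second run | yes | Denmark | no | no | – |
| Power statement, SAP 3.2 | yes | yes | no | no | BMI |

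The baseline value has support in protocol 9.2.2. Dose switch has none in the protocol, and SAP 10 does not list it as a change.

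**5. How often the model choice matters.** Simulated trials had n = 1260, 50% response and odds ratio 1.8, with a likelihood-ratio test at 0.05/136 and 2,000 replicates per case. A model with age and sex was compared with one that also had baseline MMD and dose switch. The covariate effects are assumed. *Disagree* means that only one model passes the threshold.

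| Log-odds per SD of MMD / share switching / log-odds of switching | Disagree, MAF 0.1 | Disagree, MAF 0.3 |
|---|---|---|
| −0.2 / 20% / −0.5 | 3.5% | 0.1% |
| −0.3 / 30% / −1.0 | 7.3% | 0.3% |
| −0.6 / 40% / −1.5 | 16.3% | 1.8% |

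Three further cases at MAF 0.1, with switching driven by early non-response (10% to 21% switching), gave 4.2%, 5.6% and 3.8%. A separate run of the three tabled cases (1,000 replicates) gave 2.6%, 8.4% and 16.6% at MAF 0.1 and 0% to 2.2% at MAF 0.3. The range is therefore about 3% to 16% at MAF 0.1 and about 2% or less at MAF 0.3.

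**The case against.** The best reply is that precedence is largely set. The protocol and SAP both delegate the primary analysis to Appendix B, which uses an equal split. The word *weighted* is then probably a remnant of the genome-wide plan. Appendix B still lists a reference on weighting sequence variants in whole-genome studies that its text never cites, which fits that inference. SAP 10 openly declares the move from genome-wide testing to a SNP subset, so that move is not an error. Selecting SNPs by earlier migraine findings does not depend on response in this trial, and Bonferroni naturally divides by the number tested. The robustness wording also suggests that the reduced model is the secondary run.

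Most of this stands, and it keeps the point small. It does not remove it. The weighted rule remains in the SAP's own general section, no freeze date exists, the deciding run is only implied, and dose switch is not recorded as a change.

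A reader might also infer that family-wise error is inflated. The documents do not support that. Inflation would require keeping an old divisor for a longer list, or counting a SNP when either model passes, or claiming subgroup or mPRS results as primary. No passage says any of these. Appendix B does test the mPRS and the subgroups under the primary method, but it does not call them primary findings.

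**Conclusion.** The concern holds as a minor one. The SAP contradicts itself on the form of the threshold and on whether the SNP list is closed, and its appendix puts an unrecorded post-baseline covariate in the primary model. Family-wise error is 0.05 as long as the divisor equals the number of SNPs tested. What is lost is uniqueness of the decision rule, together with possible attenuation from adjusting for dose switch.

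The contradictions rest on the text alone. The sizes do not. The 3% to 16% depends on assumed covariate effects, its upper end comes from the most extreme set, and the simulations used one pooled sample without principal components rather than the planned two-country meta-analysis. Attenuation requires that dose changes follow early response, which is plausible but not stated. The descriptive label lowers the weight of the point, but the plan still sets a 0.05 family-wise rate and makes a significance call.

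**What to change.** - **SAP 9.1:** delete *weighted* and set the threshold to 0.05/K, where K is the number of SNPs in the frozen list. Align protocol 9.3.2.2, or record the departure in SAP 10.
- **Appendix B, list:** name the K SNPs and freeze them, with a date, before database lock. Treat SNPs published later as exploratory.
- **Appendix B, model:** name as deciding the Denmark/Iceland fixed-effects meta-analysis p-value from the model with pre-treatment covariates (age, sex, baseline MMD, and a stated number of principal components in Denmark). Keep the dose-switch model as a sensitivity analysis.
- **SAP 10:** record the dropped weights, the added baseline value and the place of dose switch.
- **SAP 2.2 and protocol 3.2:** add one sentence that reconciles the no-testing statement with the 0.05 family-wise rate. Say either that this one SNP family is tested at 0.05, or that the threshold is a descriptive screening criterion.

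The cost is wording only. The one real downside is that SNPs published after the freeze cannot count in the primary family.
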